## 9 HOW SUPPLIED

- The Early Bird is supplied sterile and non-pyrogenic.

## 10 STORAGE AND HANDLING

- Store in a cool, dry place.

## 11 REQUIRED ACCESSORIES

- 0.035" (0.89 mm) Guidewire
- Heparinized Saline

## 12 DIRECTIONS FOR USE

### 12.1 Sheath Preparation

- 12.1.1 Verify the proper size introducer sheath is selected for the device to be introduced.
- 12.1.2 Verify the vessel is of adequate diameter and tortuosity to accommodate the introducer sheath.
- 12.1.3 Remove the introducer sheath and dilator from its packaging and examine contents for possible damage or defects.

**Caution: Do not use if damaged or defective.**

**Caution: Do not pull the UID battery pull tab prior to insertion of the sheath into the vasculature and prior to suturing the sheath in place. Once the battery pull tab is pulled, the device automatically powers on and allows**

**five (5) minutes for the bleed monitor to detect a bioimpedance signal before the device locks into an error state, after which, the device will not function as intended. Refer to Section 13 if the device is in an error state.**

- 12.1.4 Prior to insertion, wipe down the introducer sheath and dilator with heparinized saline. Do not wipe the surface with dry gauze.
- 12.1.5 Flush the sheath through the stopcock with heparinized saline. Close the stopcock.
- 12.1.6 Flush the dilator through the proximal hub with heparinized saline.
- 12.1.7 Carefully insert the dilator tip through the hemostasis valve and into the sheath until the dilator hub is adjacent to the hemostasis valve. Gently snap the dilator hub into the hemostasis valve housing to ensure the tapered portion of the dilator is beyond the distal end of the introducer sheath making a smooth, atraumatic transition.

## 12.2 Sheath Introduction and Use

- 12.2.1 Using standard Seldinger technique, access the target vessel with the appropriate needle.
- 12.2.2 Insert a 0.035" (0.89 mm) guidewire through the needle and into the vessel, then remove the needle ensuring the guidewire remains positioned within the vessel.
- 12.2.3 Advance the distal end of the dilator over the guidewire.
- 12.2.4 Advance the assembly (sheath/dilator) as a unit over the guidewire under fluoroscopic guidance; do not allow the dilator to back out of the sheath while advancing. Use a slight twisting motion to advance the assembly through the tissue and into the target vessel. Stop advancement of the assembly if resistance is felt. Investigate the cause of resistance before proceeding. Carefully advance the assembly until it is fully inserted.

**Caution: Do not attempt advancement of the sheath without the dilator and guidewire in place. Major bleeding, vessel damage, or serious injury to the patient, including death, may result.**

- 12.2.5 Hold the sheath steady and maintain guidewire position while withdrawing the dilator from the sheath until it is completely removed from the guidewire.
- 12.2.6 Aspirate and flush the introducer side-arm.
- 12.2.7 Carefully suture the sheath in place to minimize device movement during use.
- 12.2.8 Pull the battery pull tab to activate the Early Bird.

**Do not press the power button at this time. The power button is**

**only used to turn off the device within the first five (5) minutes.**

- 12.2.9 Carefully support all guidewires, catheters, and other devices while advancing through the valve and sheath.
- 12.2.10 Advance the selected interventional device over a guidewire through the valve and sheath. Follow manufacturer's recommendations for use of the selected interventional device.

**Caution: Do not advance or retract interventional devices into or out of the sheath if resistance is felt. Determine the cause of resistance before proceeding.**

**Caution: Do not attempt to advance sharp objects/instruments through the valve. Damage to the valve may result in major blood loss.**

**Caution: Advancement of guidewires without an appropriate wire guide through the valve may result in damage to the guidewire or the valve. Damage to the valve could lead to major blood loss.**

### 12.3 Sheath Removal

- 12.3.1 Reintroduce a 0.035" guidewire, if not already placed.
- 12.3.2 Insert the dilator over the guidewire and into the sheath and snap dilator into the sheath hub.
- 12.3.3 Gently rotate the sheath to ensure the sheath is free from the vasculature.
- 12.3.4 While maintaining the guidewire position, pull the sheath proximally until the sheath is fully removed. The yellow Device Error indicator will illuminate, and the audible indicator will momentarily beep. During removal of the sheath, precautions should be taken to prevent excessive blood loss, vessel damage, or other serious injury.
- 12.3.5 Follow standard clinical procedure to close the site after device removal.
- 12.3.6 Follow standard hospital procedure for device disposal.

## 13. FUNCTIONALITY

The Early Bird provides early detection of potential internal bleeding complications and monitors for internal bleeding progression based on baseline bioimpedance measurements and bioimpedance changes throughout the course of a procedure. The device correlates the bioimpedance signal to changes in extravascular fluid accumulation and displays bleeding status to the physician through a series of Light-Emitting Diodes (LED's) located on the UID (as shown in **Figure 2**).

**FIGURE 2: Early Bird™ UID****TABLE 2: Indicator Descriptions**

LED/Indicator	Description
Bleed Monitoring (Red) 	
The red Bleed Monitoring indicators are a series of three (3) LED's that sequentially illuminate as bioimpedance continues to change over the course of a procedure, indicating a possible internal bleeding complication.
 
 
• Level 1 indicator (1st LED) is triggered by the early onset of a bleed. An audible alert is momentarily activated once this level is triggered.
 
• Level 2 indicator (2nd LED) is triggered as the bleed progresses when a bioimpedance threshold is reached. An audible alert, longer in duration than the 1st LED, is momentarily activated once this level is triggered.
 
• Level 3 indicator (3rd LED) is triggered as the bleed continues to progress further when a higher bioimpedance threshold is reached. An audible alert is activated once this level is triggered and requires the attending physician to silence the device by pressing the silence button.
 

Low Battery (Blue)	The blue Low Battery indicator will blink when the battery is near end of life. The audible indicator will momentarily beep.

	If the system shuts down due to a low battery, the device has reserved enough power so that the system can be powered on to observe the last state of bleed monitoring indicators.
Device Error (Yellow)  	The yellow Device Error indicator will illuminate when an internal system error has been detected. The audible indicator will momentarily beep.  If the yellow Device Error is illuminated, press and hold the Power button to turn off the device and turn the device back on for one additional attempted use of bleed detection and monitoring. If the yellow Device Error illuminates again, the device cannot be used. Once the procedure is completed, report the event to Saranas.
Power (Green)  	The green Power indicator will blink after the device is first turned on and until it detects a bioimpedance signal which is in an acceptable range. Then, the indicator will stop blinking and remain illuminated throughout the procedure.
Button	Function
Silence  	This button is used to silence the audible indicator.
Power  	After the battery pull tab is pulled, the system will run through a series of self-tests which will illuminate all indicators. The audible indicator will momentarily beep.  If required, press and hold the button to turn off the device. Note that the device can be turned off only within the first five (5) minutes after powering on the device.

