## 5 CONTRAINDICATIONS

- Only one Early Bird may be used during a procedure. If more than one introducer sheath is required simultaneously to perform a procedure, use a standard introducer sheath in the secondary position.

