## 6 WARNINGS

- Carefully read all instructions prior to use. Observe all warnings and precautions noted throughout these instructions. Failure to do so may result in complications.
- Only physicians who have received appropriate training and are familiar with the principles, clinical applications, side effects and hazards commonly associated with vascular interventional procedures should use this device.
- This device is not MRI compatible.
- The Early Bird may not detect an Internal Bleeding Complication if internal bleeding has already occurred prior to insertion of the introducer sheath or prior to initial bioimpedance measurement.
- The Early Bird should not be exposed to organic solvents.
- Do not alter this device, including cutting to alter the length. Alterations may impair device function.
- Do not attempt to place a guidewire with a maximum diameter greater than 0.035" (0.89 mm) through the dilator.
- Do not attempt to insert a catheter or interventional device having a diameter larger than the introducer sheath size (Table 1). Device damage or breakage may result.
- Do not attempt to insert multiple catheters or interventional devices when the combined diameter is larger than the introducer sheath size (Table 1). Device damage or breakage may result.
- Do not attempt sheath advancement or withdrawal without guidewire and dilator in place. Major bleeding, vessel damage or serious injury to the patient, including death, may result.

- Adequate vessel access is required to introduce the sheath into the vasculature. Careful evaluation of vessel size, anatomy, tortuosity, and disease state (including calcification, plaque, and thrombus) is required to ensure successful sheath introduction and subsequent withdrawal. If the vessel is not adequate for access, major bleeding, vessel damage, or serious injury to the patient, including death, may result.
- Do not advance the sheath if the dilator is not snapped in the hemostasis valve housing. When the dilator is not snapped into the valve housing, the tip of the introducer sheath may not be fully supported by the cylindrical section of the dilator. Therefore, advancement of the unsupported tip of the introducer sheath may result in major bleeding, vessel damage, or serious injury to the patient, including death.

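### The IFU's only recovery step for a device error contradicts its own five-minute switch-off limit, and the analysis has no rule for subjects whose monitoring fails

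*Combined protocol and SAP*

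**What the plan says.** Protocol 4.3.2 makes the IFU the operating procedure for introducing the device. On errors the IFU says:

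- **Section 13, Table 2, Device Error row:** the user is to "press and hold the Power button to turn off the device and turn the device back on for one additional attempted use". After a repeat, "If the yellow Device Error illuminates again, the device cannot be used", and the event goes to the sponsor.
- **Section 13, Table 2, Power button row:** "Note that the device can be turned off only within the first five (5) minutes after powering on the device".
- **12.2, note after step 12.2.8:** the power button is "only used to turn off the device within the first five (5) minutes".
- **12.1, caution after step 12.1.3:** once the battery tab is pulled there are "five (5) minutes for the bleed monitor to detect a bioimpedance signal before the device locks into an error state". A user facing an error state is referred to Section 13.
- **Section 5, Contraindications:** "Only one Early Bird may be used during a procedure".

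Protocol 4.3.3 continues monitoring for up to 8 hours after the procedure. On the analysis side:

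- 6.6.2 reduces each case to bleed or no bleed by each technique.
- 6.5 defines the per-protocol (PP) set by having a post-procedure CT.
- 6.6.4 makes one missing-data exception, for a missing CT.
- 5.4 has device deficiencies and malfunctions recorded on the CRF.

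**The concern.** The device reading is the index test, and the IFU is its operating rule. Where that rule contradicts itself, sites that meet the same error may act differently: attempt a power cycle, stop monitoring, or consider another device. Some subjects would then have device monitoring that covers only part of the period at risk.

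The statistical consequence is an undefined result. A device that failed before a bleed gives no alarm, and so does a device that watched throughout and correctly saw nothing. Nothing in section 6 separates the two. If the choice between scoring such a subject as no bleed, excluding the subject or calling the result unevaluable is left until the data are in, it will be made with the CT result visible. With about five bleeds expected in 100 subjects, that choice can matter for a single subject.

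**Working it through.** **1. The IFU passages side by side**

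| Time since power-on | Event | What the IFU offers |
|---|---|---|
| Within 5 minutes | Device error | Off and on, one further attempt; consistent with the switch-off limit |
| 5 minutes, no signal | Error state locks | Referral to Section 13, whose step is off and on, as the switch-off window ends |
| After 5 minutes, through the procedure and up to 8 hours beyond | Device error | The same step, but the device can no longer be switched off |

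Neither statement of the limit (Power button row, 12.2) makes an exception for an error state, and the Device Error row carries no time limit. As written, both cannot hold after five minutes.

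**2. From the device to the primary analysis**

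A subject has a device error after five minutes and no alarm, and a post-procedure CT is done. The CT puts the subject in the PP set (6.5). Section 6.6.2 requires bleed or no bleed for the device. The exception in 6.6.4 does not apply, because the CT is present. Section 5.4 puts the malfunction on the CRF but does not connect it to 6.6.2. The only dichotomous value at hand is no bleed.

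**3. Reproducing the plan's figure**

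Inputs from protocol 6.1: 100 subjects, 5 with a bleed by either method, 2 discordant pairs. Take both positive 3, device only 1, CT only 1, both negative 95 (written 3/1/1/95). Kappa = (po − pe)/(1 − pe).

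- po = (3 + 95)/100 = 0.98
- pe = 0.04 × 0.04 + 0.96 × 0.96 = 0.9232
- kappa = 0.0568/0.0768 = 0.74

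The large-sample (Fleiss-Cohen-Everitt) standard error gives a 95% interval of 0.39 to 1.0 with the upper limit cut at 1. This matches section 6.1.

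**4. Illustration: one detection lost to a device error and scored no bleed**

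The table becomes 2/1/2/95.

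- po = 0.97
- pe = 0.03 × 0.04 + 0.97 × 0.96 = 0.9324
- kappa = 0.0376/0.0676 = 0.56 (95% interval 0.11 to 1.0)
- sensitivity against CT falls from 3/4 = 75% to 2/4 = 50%

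A second lost detection (1/1/3/95) gives kappa 0.32.

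The starting table matters. If all 5 bleeds are CT-positive and the device gives no false alarms, losing 1, 2 or 3 detections gives kappa 0.88, 0.74 or 0.56. From that start it takes three losses to fall below 0.6.

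**5. How far the scoring choice alone moves the result**

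For the single affected CT-positive subject in step 4:

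- counted as no alarm, 2/1/2/95: kappa 0.56
- counted as alarm, 3/1/1/95: kappa 0.74
- excluded, 2/1/1/95 with n = 99: po = 97/99 = 0.9798; pe = (3/99)² + (96/99)² = 0.9412; kappa = 0.66, sensitivity 2/3 = 67%

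The same subject gives kappa between 0.56 and 0.74, on both sides of 0.6, according to a rule that the plan does not state.

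**The case against.** The five-minute limit may have been meant for normal operation, with power-off still possible in an error state. That is a fair guess at intent, but neither statement of the limit says so. If it is the intent, the IFU has to say it.

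Some provisions do exist. A repeat error has an end point and goes to the sponsor. Section 5.4 captures malfunctions, and 4.3.3 returns the device for assessment of its impedance response. These stand, and they mean that part of the information will be available. They do not say how the subject is scored.

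The one-device contraindication is followed by a sentence about sheaths needed simultaneously, so it may not bar a sequential replacement. This also stands: the text is unclear on the point.

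The kappa shift is what any single lost detection does to a table with so few bleeds. That is correct, so it shows fragility and not expected impact.

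A reader might go further in four ways that the documents do not support:

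- **That a restart takes a new baseline and absorbs blood already present.** Protocol 2.2 says only that baseline readings follow insertion, and IFU Section 6 warns that "The Early Bird may not detect an Internal Bleeding Complication if internal bleeding has already occurred prior to insertion" or before the initial measurement. No passage says what a restart does to the baseline. Table 2 lets the last indicator state be viewed after a low-battery shutdown, so some state survives. Under the written limit a restart is possible only in the first five minutes, so bias from late restarts presupposes what the IFU rules out.
- **That five minutes as a share of the 12-hour battery life measures the problem.** It is a ratio of times, not an error rate, and the only error with a stated time is the start-up lock.
- **That the error light at removal inflates complication counts.** Step 12.3.4 says that at removal "The yellow Device Error indicator will illuminate, and the audible indicator will momentarily beep". Section 5.4 defines a malfunction as departure from what the IFU describes, so this expected light is not one.
- **That dropping restarted subjects with no alarm would repair the analysis.** This selects on the index-test result: missed bleeds leave while restarted false alarms stay. In step 5, dropping the missed bleeder lifts kappa from 0.56 to 0.66.

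**Conclusion.** The contradiction is in the current text and can be checked by reading the IFU passages together. The Device Error step and the switch-off limit conflict for any error after the first five minutes, and the start-up error sends users to that step as the window closes. The statistical gap is equally plain: no rule covers a device error, a restart or incomplete monitoring in the kappa, sensitivity or specificity.

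The size is unknown because no device-error rate is given. The fall from 0.74 to 0.56 assumes the section 6.1 scenario, one error that coincides with a bleed, and scoring as no bleed. The 0.6 level is a descriptive benchmark in 6.6.2, so what is at stake is interpretation, not a formal test.

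This should be settled before enrolment. Which device rule is right is for the sponsor, and nothing here favours one.

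**What to change.** 1. **IFU and protocol 4.3.** Reconcile IFU 12.1, 12.2, Section 13 Table 2 (both rows) and Section 5 into one device-error instruction, including whether a sequential replacement is allowed. The sponsor settles the content. State also whether a restart resets or keeps the baseline.
2. **CRF.** Record the time of any device error, any restart and its time, and the end of valid monitoring.
3. **Section 6.6.2.** Fix in advance the scoring of subjects with a device error, restart or incomplete monitoring. Keep any alarm reached before the error as that subject's device result, and report the number affected. Repeat kappa, sensitivity and specificity in two ways: (a) excluding all affected subjects, whatever their alarm result; (b) counting affected subjects with no alarm once as alarm and once as no alarm. Exclusion should not stand alone, because it can itself raise kappa, as step 5 of the working shows.

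The cost is IFU and protocol wording, a few CRF fields and a sensitivity analysis. No procedures are added for subjects.

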#### 14. TECHNICAL DESCRIPTION

##### Battery

Battery Type: Alkaline 1.5V AAA

Battery Life: Up to 12 hours

The Early Bird battery is non-serviceable.

### **Electrical Safety**

ME Equipment Class: Internally Powered

Patient Connection: Type BF

The Early Bird Bleed Monitoring System (User Interface Display module and introducer sheath) is considered to be the Applied Part.

### **Electromagnetic Compatibility (EMC)**

The Early Bird meets the requirements of IEC 60601-1-2 for a Group 1, Class A device. Specific levels for the Early Bird device appear below.

**TABLE 3: Electromagnetic Emissions**

Guidance and Manufacturer's Declaration – Electromagnetic Emissions		
Emissions Test	Compliance	Electromagnetic Environment - Guidance
RF Emissions CISPR II	Group 1	The Early Bird uses RF energy only for its internal function. Therefore, its RF emissions are very low and are not likely to cause any interference to nearby electronic equipment.
RF Emissions CISPR II	Class A	The Early Bird is suitable for use in all establishments other than domestic and those directly connected to the public low-voltage power supply network that supplies buildings used for domestic purposes.

**TABLE 4: Electromagnetic Immunity**

Guidance and Manufacturer's Declaration – Electromagnetic Immunity			
Immunity Test	IEC 60601 Test Level	Compliance	Electromagnetic Environment - Guidance
			The Early Bird is intended for use in the electromagnetic environment specified below. The customer or the user of the Early Bird should assure that it is used in such an environment.

Electrostatic Discharge IEC 61000-4-2	No false indications, error mode allowed: 8 kV Contact 15 kV Air	Complies	Floors should be wood, concrete or ceramic tile. If floors are covered with synthetic material, the relative humidity should be at least 30 %.
Power frequency (50/60 Hz) magnetic field IEC 61000-4-8	30 A/m 50 or 60 Hz	Complies	If abnormal operation occurs, it may be necessary to position the Early Bird further from sources of power frequency magnetic fields or to install magnetic shielding. The power frequency magnetic field should be measured in the intended location of use to assure that it is sufficiently low.
Conducted RF IEC 61000-4-6	3V 0.15 to 80 MHz 6V in ISM bands between 0.15 and 80 MHz 80% AM at 1 kHz	Refer to TABLE 5	
Portable and mobile RF communications equipment should be used no closer to any part of the Early Bird, including cables, than the recommended separation distance calculated from the equation applicable to the frequency of the transmitter.
 
Recommended separation distance  <math>d = 1.2 \sqrt{P}</math> 150 kHz to 80 MHz  <math>d = 1.2 \sqrt{P}</math> 80 MHz to 800 MHz  <math>d = 2.4 \sqrt{P}</math> 800 MHz to 2.5 GHz
 
where P is the maximum output power rating of the transmitter in watts (W) according to the transmitter manufacturer and d is the recommended separation distance in meters (m).
 
Field strengths from fixed RF transmitters, as determined by an electromagnetic site surveya, should be less than the compliance level in each frequency rangeb.

Radiated RF IEC 61000-4-3	3 V/m 80 MHz to 2.7 GHz 80% AM at 1 kHz	Refer to TABLE 5	

			
Interference may occur in the vicinity of equipment marked with the following symbol:
 

NOTE 1: These guidelines may not apply in all situations. Electromagnetic propagation is affected by absorption and reflection from structures, objects, and people.
			

a Field strengths from fixed transmitters, such as base stations for radio (cellular/cordless) telephones and land mobile radios, amateur radio, AM and FM radio broadcast and TV broadcast cannot be predicted theoretically with accuracy. To assess the electromagnetic environment due to fixed RF transmitters, an electromagnetic site survey should be considered. If the measured field strength in the location in which the Early Bird is used exceeds the applicable RF compliance level above, the Early Bird should be observed to verify normal operation. If abnormal performance is observed, additional measures may be necessary, such as relocating to an alternate site.
 
b Over the frequency range 150 kHz to 80 MHz, field strengths should be less than 3 V/m.
			

